5.1. General

The Relivion™ is an external neurostimulator designed for transcutaneous electrical nerve stimulation. The headset integrates three pairs of output electrodes which come in contact with the subject scalp at the forehead (two pairs) and occiput (1 pair). The electrodes deliver the stimulation pulses produced by the stimulation unit to the subject's scalp. The frontal electrodes stimulate the trigeminal (supraorbital & supratrochlear) nerve branches and the posterior electrodes stimulate the occipital nerve branches (**Figures 1 and 2** below). Stimulation intensity can be adjusted by the user.

The Relivion™ is a prescription device that will be self-used in a home environment.

[figure not shown]

Figure 1: Relivion™ and its target nerves

Figure 2: Relivion™ on a user

The device is comprised of a headset with integrated electrodes, designed to enable stimulation of the target nerves. The on-board stimulation circuit is adapted to deliver stimulation patterns to enhance proper nerve activation. The headset adjusts to various head sizes and contours and can be worn

 Neurolief Brain Innovation	THE RIME STUDY: ABRIDGED CLINICAL INVESTIGATION PLAN	Doc No.: CL-CIP-001 Abridged Ref Rev: REV.2 / 11JUN2019 Pg. 17 of 41
--	---	--

comfortably. Each time the headset is worn, the six electrodes are placed over the underlying nerves. Four anterior forehead electrodes are aligned with branches of the trigeminal nerve (supraorbital & supratrochlear) and two posterior electrodes are aligned with the greater occipital nerve branches. The headset includes two flexible arms that penetrate under the hair layers while the headset is donned. A size adjustment mechanism is located at both sides of the headset. It enables adjustment of the headset size to the head of the user before first use. The Relivion™ includes six replaceable electrode pads that are positioned above the headset electrodes. The pads consist of a water absorbing foam and should be wetted by the user before each use in order to provide proper conductivity between the electrodes and the scalp. Water releasing covers are located on the outer side of each occipital electrode. After positioning the headset on the head, the user press once on the water release covers to release moisture from the electrode pads onto the scalp, thereby maintaining conductivity between the electrodes and the scalp. The Relivion™ incorporates an on-board interface that enables the user to activate/deactivate the device and to adjust the stimulation intensity. It also provides visual and auditory indications such as whether the device is active/non-active and when there is a low battery.

The Relivion™ can communicate via a low energy Bluetooth link with a mobile application on the user's smartphone. The mobile application displays the device status and provides indications and alerts such as treatment intensity level, treatment duration, low battery, charging state, etc. The mobile application is optional as the Relivion™ can be fully operated without it. Furthermore, the device cannot be controlled (activate, adjust intensity, etc.) by the mobile application.

Further details, images and specifications are provided in the User Manual.

5.2. Mode of Action

As explained, the Relivion™ is an external neurostimulator designed for transcutaneous electrical nerve stimulation. The headset integrates three pairs of output electrodes which come in contact with the subject skin at the forehead and occiput. The electrodes deliver the stimulation pulses produced by the stimulation unit to the subject's scalp. The frontal electrodes stimulate the trigeminal (supraorbital and supratrochlear) nerve branches and the posterior electrodes stimulate the greater occipital nerve branches.

Overactive pain and symptom areas of the brain are believed to play a primary role in the onset of migraines [20]. The Relivion™ device treats migraine by stimulating the trigeminal and occipital nerve branches, thereby reducing the overactive pain-and-symptom areas and altering the activity in pain-associated central structures.

5.3. Dosage Form

For purposes of this study, the Relivion™ will be provided in therapeutic and non-therapeutic modes, to accommodate for the Active and Sham groups:

- Group A – Active Treatment: For the therapeutic mode the device will be preset to the following parameters: stimulation waveform- symmetrical biphasic, phase duration 330-400 microseconds, pulse frequency 80Hz, trigeminal stimulation intensity – up to 6mA, Occipital stimulation intensity– up to 12mA.
- Group B – Sham Control: For the non-therapeutic mode the device will be preset to the following parameters: Stimulation waveform- symmetrical biphasic, phase duration- 70-100 microseconds, pulse frequency 0.33 Hz, trigeminal stimulation intensity up to 5mA, occipital stimulation intensity up to 10mA.

Both Active and Sham stimulation devices are packaged and labeled identically to maintain blinding of both the subject and study staff.

Each Relivion treatment will last 60 ± 30 minutes. The Relivion device programmed treatment duration will be 1 hour. In case an earlier substantial pain relief is achieved, subject may stop treatment earlier.

5.4. Intended Use & Intended Population

The Relivion™ transcutaneous electrical nerve stimulator is intended for the treatment of headache and is indicated for the acute treatment of migraine with or without aura in patients 18 years of age or older. It is a prescription device to be self-used at home.

6. Study Design

6.1. General

Multi-center, prospective, 2-arms randomized, double-blind, parallel-group, sham controlled study evaluating the safety and efficacy of the Relivion™ in subjects 18 years of age and older suffering from migraine headache with and without aura. The study will include the following periods:

1. Run-in Period (28 days)
2. Randomization to Active Relivion vs. Sham control treatment arm (1:1 randomization) and Self-Practice Period (Up to 14 days)
3. Treatment Period (up to 5 migraine attacks or 70 ± 10 days from Randomization visit, whichever comes first)

After completion of the Treatment Period the subject's participation will be over.

Study flowchart is summarized in **Figure 4** and details of the assessments to be completed at each period / visit are provided in **Section 9**.

The planned number of subjects is 200. There are no procedures for the replacement of subjects.

The study will be conducted at a maximum of 12 investigational sites in the US and Israel; Sites in the US will enroll approximately 33% of total subjects. Each site will enroll a maximum of 60 subjects.

[figure not shown]

Figure 3: Study Flowchart

 Neurolief Brain Innovation	THE RIME STUDY: ABRIDGED CLINICAL INVESTIGATION PLAN	Doc No.: CL-CIP-001 Abridged Ref Rev: REV.2 / 11JUN2019 Pg. 20 of 41
--	---	---

6.2. Randomization

Subjects will be prospectively randomized into the clinical study. Randomization will occur only after the subject provides informed consent, completes the Run-in Period and all required screening and baseline procedures, and satisfies the study eligibility criteria.

6.3. Measures to Minimize Bias

Several measures will be implemented to minimize systematic error/bias:

- Randomization to active treatment vs. sham control.
- Blinding of both subjects and study personnel.
- At the end of Visit 2, before starting the self-practice, subjects will be asked for their opinion concerning their group assignment. Their response will be documented in the CRF.
- Screening log will be completed by investigational sites listing all migraine patients consented to the RIME study. The log will include reasons for exclusion from the study.
- Pain assessment will be performed using a subject diary.
- Investigator's reported serious adverse events and device related adverse events will be reviewed and adjudicated, if required, by Neurolief and if needed forwarded to the company's medical advisor for further review and assessment. The adjudicated results will be updated in the study CRF and used in all cases for purposes of data analysis.
- Medical monitoring will take place in reviewing safety data and ensuring appropriate reporting of adverse events. The sponsor, the Medical advisor and Principal Investigator will oversee the overall safety of the study.
- Clinical monitors will verify patients' data and ensure compliance with good clinical practice (GCP), CIP and other study requirements.

7. Selection of Subjects

7.1. Study Population

The study will include male and female subjects, 18 years of age and older suffering from migraine headache with and without aura.

7.2. Subject Enrollment

A maximum of 200 subjects will be enrolled to the study. Subjects will be assessed, treated and followed as per the requirements listed in **Table 1**.

Adults known to the clinic as suffering from migraine, or subjects referred to the clinic, or subjects who approach the clinic due to study approved advertising may be recruited for inclusion in the study. After being informed of the nature of the study, the subject will sign a written informed consent form (ICF) that has been approved by the Sponsor and the appropriate IRB/ EC of the respective clinical site or the

 Neurolief Brain Innovation	THE RIME STUDY: ABRIDGED CLINICAL INVESTIGATION PLAN	Doc No.: CL-CIP-001 Abridged Ref Rev: REV.2 / 11JUN2019 Pg. 21 of 41
--	---	--

central IRB/EC, during the screening visit. Written, informed consent will be obtained for all patients who are potential study candidates prior to applying any study specific assessment to the subject or any data collection. See **Section 9.4** for details on subject informed consent procedure.

Refer to **Figure 1** for a summary of the study schedule of assessment. Specifically, subjects will be evaluated at Visit 1 to assess whether they meet study eligibility criteria. Those meeting all of the inclusion and none of the exclusion criteria will initiate the Run-In Period for 28 days (+10 days). Subjects will return for Visit 2 (Day 0) for a repeat assessment of eligibility. Those found eligible will be enrolled and randomized. A subject is considered enrolled in the study when it is determined that all inclusion/exclusion criteria are met during visit 2 and after run-in period diary is assessed. At this point they will undergo device, device app and Patient Reported Outcome (PRO) training and will be asked to complete the blinding assessment. Subjects will be sent home with the device and the study dedicated smartphone for a 2 weeks Self-Practice Period. During these 2 weeks they will perform 2 self-training treatment sessions, not during a Migraine attack and complete the PRO. Device logs will be verified by the study team during Visit 3 (potentially remote verification). Subjects with at least 1 self-training session completed successfully will be approved by site team to initiate the Treatment Period and to treat at least 1 and up to 5 migraine episodes, within up to 70+10 days from visit 1, whichever comes first. Once completing the Treatment Period, they will return for end of study visit (Visit 4) during which the device will be returned, final data will be collected and the subjects will be exited from the study.

Subjects found ineligible by the procedures required at screening will be marked as 'screen failure' on the screening & enrollment log and will not take part in the study. Screen failure subjects will not be included in the intention-to-treat analysis, nor will they be counted as part of the target subject sample number.

7.3. Inclusion Criteria

In order to be included in the RIME study patients must fulfill all of the inclusion criteria.

1. Subjects 18 years of age and older.
2. Subject meets the ICHD-3 (2018) diagnostic criteria for Migraine with or without aura.
3. Subject reports 1-6 Migraine attacks per month; other headaches no more than 6 days per month.
4. Subject is willing to and capable of complying with the specified study requirements, provided written Informed Consent, can complete the electronic diaries, and can be contacted by telephone.

7.4. Exclusion Criteria

In order to be included in the RIME study patients must fulfill none of the exclusion criteria.

1. Subject having received Botox treatment in the head region in the prior 3 months.
2. Subject having received supraorbital or occipital nerve blocks in the prior month.

3. Past 6 months of chronic migraine, New Daily Persistent Headache, and chronic tension-type headache per ICHD-3 (2018) diagnostic criteria.
4. Subject has >10 headache days per month
5. Current medication overuse headache.
6. Use of opioid medications in the prior 1 month.
7. Use of barbiturates in the prior 1 month.
8. Implanted metal/shrapnel or electrical devices in the head (not including dental implants), a cardiac pacemaker or an implanted or wearable defibrillator.
9. Received parenteral infusions for migraine within the previous 2 weeks.
10. Subject has known uncontrolled epilepsy.
11. History of neurosurgical interventions
12. Subject with implanted neurostimulators, surgical clips (above the shoulder line) or any medical pumps.
13. Current drug abuse or alcoholism.
14. Subject is participating in any other clinical study.
15. Skin lesion or inflammation at the region of the stimulating electrodes.
16. Personality or somatoform disorder.
17. Pregnancy or Lactation.
18. Women with child bearing potential without medically acceptable method of contraception (NOTE: Females of child bearing potential must have a negative pregnancy test).
19. Documented history of cerebrovascular event.
20. Subject with recent brain or facial trauma (occurred less than 3 months prior to this study).
21. Subject participated in a previous study with the Relivion device.
22. The subject does not have the basic cognitive and motor skills needed to operate a smartphone.
23. Subject with head circumference smaller than 51 centimeters or head circumference larger than 60 centimeters
24. Subject with other significant pain problem that in the opinion of the investigator may confound the study assessments.

8. Study Procedures

8.1. Schedule of Events

The schedule of events is depicted in **Table 1** and **Figure 1**.

Table 1: Schedule of Events

Visit	Visit 1	Run-In Period	Visit 2	Self-Practice Period	Visit 3	Treatment Period	Visit 4
Event / Timeline	Day -28	-28 +10 days from Visit 1	Day 0	up to Day 14	remote; Up to Day 14	Up to 5 episodes / Day 70+10	Up to 5 episodes / Day 70+10
Written Informed Consent	X						
Eligibility assessment	X		X				
3-month migraine retrospective history questionnaire	X						
Medical history & Demography	X						
Prophylactic anti-migraine & rescue headache medication	X			X ¹			X ¹
Physical examination ² & Vital signs	X						
Documented significant change in health status (e.g., surgery, accident, MI)			X				
Pregnancy test ³	X		X				
Run-in Diary		X					
Enrollment & Randomization			X				
Device and PRO ⁴ training			X				
Device and PRO Self-practice			X	X			
Blinding assessment questionnaire			X				
Device logs and PRO verification			X ⁵		X		X
Active / sham treatment						X	
Diary PRO at baseline, 1, 2 & 24 hr post treatment						X	
Global Impression of Effect questionnaire							X
Adverse events			X				X
End of study							X

1 Document change in medications

2 Physical exam to include: Head, eyes, ears, nose, throat (HEENT), Lungs, Heart and Neurologic exam; Vital signs include blood pressure, pulse and respiratory rate

3 Pregnancy test for women of childbearing potential only

4 PRO: Patient Reported Outcome

5 Device logs only at Visit 2

8.1.1. Visit 1 - Run-in (day -28)

Written below are the assessments to be completed at Visit 1:

- Written informed consent.
- Eligibility assessment.
- 3-month migraine retrospective history questionnaire.
- Prophylactic anti-migraine & rescue headache medication (all medications, preventive, prescribed acute, and over the counter are to be recorded).
- Medical history & Demography.
- Physical exam, including Head, eyes, ears, nose, throat (HEENT), Lungs, Heart, Neurologic exam and Vital signs including blood pressure, pulse and respiratory rate.
- Pregnancy test (for women of childbearing potential).
- Run-in Period diary dispensing and training.

The research coordinator will review the study requirements with the subject to help ensure compliance. Telephone numbers must be obtained from the subject to ensure the ability to contact him/her.

8.1.2. Run-In Period (Day 0 -28+10 days)

- Completion of the Run-In Diary by the subject during the run-in period. A Subject who failed to complete the required information on the Run-In Diary will be considered a screen failure. The diary will capture information with respect to frequency, intensity and duration of migraine episodes, existence of aura and other symptoms, use of rescue medications, and other types of headaches. Two (2) different Migraine episodes will be defined by, at minimum, by 48 hours free of pain in between.
- Study team may contact the subject periodically to remind him/her to fill in the diary

8.1.3. Visit 2 - Randomization (28+10 days from Visit 1)

Written below are the assessments to be completed at Visit 2:

- Review of Run-in Diary.
- Change in prophylactic anti-migraine & rescue headache medication will be documented.
- Documented significant change in health status (e.g., surgery, accident, MI)
- Pregnancy test (women of childbearing potential only).
- Verification of eligibility.
- Randomization to Group A (Active Treatment) and Group B (Sham Control).
- Subject will read the User manual and watch the instructional video and be trained on the device by the study team.
- Device size will be adjusted to subject head circumferences.

 Neurolief Brain Innovation	THE RIME STUDY: ABRIDGED CLINICAL INVESTIGATION PLAN	Doc No.: CL-CIP-001 Abridged Ref Rev: REV.2 / 11JUN2019 Pg. 25 of 41
--	---	--

- Subject will self-practice the device along with the mobile application to become familiar with its use and with the stimulation.
- Blinding Assessment questionnaire.
- Subject will be trained on the Patient Reported Outcome (electronic/hard copy) diary for documenting the outcome measures and rescue medication intake.
- Mobile application/Device logs verification for stimulation intensity. Stimulation intensity to be above 2mA. In case subject fail to reach a minimum stimulation intensity of 2mA, subject will be withdrawn.
- Subject will be provided with the device, a dedicated smartphone, a subject's instruction form and Patient Reported Outcome diary (electronic/hard copy) for up to 14 days Self-Practice period at their home.
- Adverse events occurring during the visit will be documented.

8.1.4. Self-Practice Period (up to 14 days)

- Subject's self-practice of the device and Patient Reported Outcome diary twice, not during a migraine episode, for 30-60 minutes. Device Logs will be automatically uploaded by the mobile application to the study cloud-based database.
- Study team may contact the subject periodically to remind him/her to perform self-practice procedure.
- Subject will notify study team once completing 2 self-practice sessions.

8.1.5. Visit 3 (remotely or clinic visit; up to day 14)

Written below are the assessments to be completed at Visit 3:

- A visit is needed in case device logs were not download to the study cloud-based database, otherwise a remote contact is allowed.
- Upon subject notification of the completeness of 2 self-practice sessions:
 - Study team will confirm within device logs that the subject completed at least one self-practice session successfully. Device logs shall present Subject's study code, Device serial number, Date of stimulation session, stimulation session timeline bar presenting stimulation events such as "pass", "fail", Device failure events. A stimulation session marked as "Pass" if a minimal stimulation of 2 mA was delivered, or "Fail" if a minimal stimulation of 2 mA was not delivered. An eligible self-practice session will be defined by a recorded device log with a stimulation duration of at least 30 minutes of a "Pass" session in the device log.
 - Study team will verify correct reporting on PRO and inform/retrain subject on correct PRO reporting, if required.
 - If at least one self-practice session completed successfully, study team will contact the subject and guide him/her to use the device during up to 5 migraine episodes within up to day 70+10 from Visit 2.
 - Call will be documented and will be considered as remote study Visit 3.

- If both self-practice sessions are non-eligible, subject will be withdrawn from the study. Study team will call the subject and invite him/her to a study termination visit. Subject invitation will be considered as remote study Visit 3, termination visit will be documented.

8.1.6. Treatment period (up to 5 treated Migraine episodes or day 70±10 whichever comes first)

- Subjects will use the device for at least 1 and up to 5 migraine episodes within up to day 70±10 from visit 2, whichever comes first.
- Subjects will be instructed to differentiate between 2 different Migraine episodes which will be defined by, at minimum, 48 hours free of pain in between.
- Study team will contact the subject periodically to remind him/her to use the device during his/her next migraine episode.
- Study team will periodically verify device logs of treated attacks on the study cloud database and may contact the subject for re-training if required.
- Subject will use the device at home or surroundings immediately upon the initiation of the Migraine headache and no later than 30 minutes afterwards:
 - Subject will initiate the treatment procedure by turning on the device and the dedicated mobile application. The mobile application will guide the subject through the treatment procedure steps and will direct him/her to the study Patient Reported Outcome diary when required.
 - Prior to initiating the treatment, subject will report on the Patient Reported Outcome diary that:
 - He/she did not use analgesics or other pain relief drugs or cannabis within 4 hours period before the treatment.
 - Confirm no more than 30 minutes have passed since Migraine episode headache initiated.
 - Confirm that at least 48 pain free hours have passed since the subject previous Migraine episode.
 - Confirm he/she did not wake up with a Migraine headache.
- In case subject used analgesics or other pain relief drugs or cannabis within 4 hours period before the treatment initiation and/or more than 30 minutes passed from the start of the migraine episode and/or less than 48 pain free hours have passed since subject's previous Migraine episode and/or subject woke up with a Migraine headache, subject will be instructed to refrain from using the device and await his/her next migraine episode.
- Prior to initiation of treatment and no later than 30 minutes from Migraine headache pain initiation, subject will document on the Patient Reported Outcome diary his/her baseline migraine pain level (whereas 1=Mild pain, 2=Moderate pain, 3=Severe pain) and the most bothersome migraine-associated symptom (nausea, photophobia, phonophobia or none).
- Subject will then initiate the treatment along with the dedicated mobile application. The treatment will last 60±30 minutes. The Relivion™ device programmed treatment duration will be 1 hour. In case an earlier substantial pain relief is achieved, subject may stop treatment earlier but not less than 30 minutes from treatment start. If necessary, treatment can be paused by the

 Neurolief Brain Innovation	THE RIME STUDY: ABRIDGED CLINICAL INVESTIGATION PLAN	Doc No.: CL-CIP-001 Abridged Ref Rev: REV.2 / 11JUN2019 Pg. 27 of 41
--	---	--

subject and then be resumed. Treatment with total stimulation time of at least 30 minutes of a "pass" session on the device log timeline, will count as a completed treatment.

- Subjects will be asked to refrain from consuming rescue medication/cannabis for at least 2 hours post treatment initiation. Subjects using rescue medication/cannabis prior to 2 hours post treatment initiation will be considered as failure (will be assigned the value of 0=no headache pain reduction) in the primary analysis.
- Subjects will document on the Patient Reported Outcome diary:
 - Pain according to a 4 points scale (0=no pain, 1=Mild pain, 2=Moderate pain, 3=Severe pain) at 1 and 2 hours \pm 30 minutes and at 24 hours \pm 6 hours post initiation of treatment.
 - Most Bothersome migraine-associated Symptom (MBS) other than a headache (chosen at baseline) improvement (yes/no) at 1 and 2 hours \pm 30 minutes post-treatment initiation.
 - Rescue medication intake.

8.1.7. Visit 4 - Termination visit (following 5 treated Migraine episodes or day 70 \pm 10, whichever comes first)

Written below are the assessments to be completed at Visit 4:

- After up to 5 migraine episodes within up to day 70 \pm 10, whichever comes first, subject will report to the clinic and return the device, Smartphone and hard copy subject diary, if applicable.
- Change in prophylactic anti-migraine & rescue headache medication will be documented.
- Subjects device Global Impression of Effect will be documented.
- Adverse events will be documented.
- Device logs, for each Migraine treated episode, will be downloaded by the study team (from study cloud database or from the device) to ascertain eligible treatments. An eligible treatment is defined as:
 - treatment meeting the basic criteria (*i.e.*, no analgesics or other pain relief drugs or cannabis within 4 hours period before the treatment initiation; no more than 30 minutes passed from the start of the migraine episode; more than 48 pain free hours have passed since subject's previous Migraine episode; and subject did not wake up with a Migraine headache); and
 - with total stimulation time of at least 30 minutes of a "pass" session on the device log timeline, where pass is defined as a minimal stimulation of 2mA delivered).

The characteristics of each treatment will be indicated on the subject CRF.

At this point subject's participation in this study will be over. The subjects will continue receiving medical care as per local standard of care, but not within the clinical study. Adverse Events that are still ongoing will be followed per local standard of care, but not within the clinical study.

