4.2.2. Secondary Efficacy Endpoints

1. Proportion of subjects reporting improvement in their MBS other than a headache, 2 hours post-treatment initiation (if rescue therapy was not used), in their first eligible treated migraine attack. MBS may be nausea, photophobia, phonophobia as defined by each subject prior to beginning of the treatment.
2. Proportion of subjects reporting reduction of migraine headache pain 1-hour post treatment initiation (if rescue therapy was not used), from severe or moderate to mild or no pain, or from mild to no pain, in their first eligible treated migraine attack.
3. Proportion of subjects who are pain free at 2 hours post treatment initiation (if rescue therapy was not used), in their first eligible treated migraine attack.

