11.1.2. Secondary endpoint variables

The three secondary endpoints will also be represented in the form of binary variables which will be assigned the value of "1" if the subject is a "responder" to each specific secondary endpoint, and "0" otherwise.

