Secondary efficacy endpoints include:

1. Proportion of subjects reporting improvement in their most bothersome migraine-associated symptom (MBS) other than a headache, 2 hours post-treatment initiation (if rescue therapy was not used), in their first eligible

treated migraine attack. MBS may be nausea, photophobia, phonophobia as defined by each subject prior to beginning of the treatment.

2. Proportion of subjects reporting reduction of migraine headache pain 1-hour post treatment initiation (if rescue therapy was not used), from severe or moderate to mild or no pain, or from mild to no pain, in their first eligible treated migraine attack.
3. Proportion of subjects who are pain free at 2 hours post treatment initiation (if rescue therapy was not used), in their first eligible treated migraine attack.

2.3

Additional efficacy endpoints

1. Proportion of subjects reporting freedom from their MBS other than a headache, 2 hours post-treatment initiation (if rescue therapy was not used), in their first eligible treated migraine attack.
2. Proportion of subjects who are pain free at 1-hour post treatment initiation (if rescue therapy was not used), in their first eligible treated migraine attack.
3. Proportion of subjects rating the subjects positive (score of 4 or 5) Global Impression of Effect of study device at the end of the study, defined as satisfied or very satisfied using a simple Likert-type scale whereas 1 = Very dissatisfied, 2 = dissatisfied, 3 = unsure, 4 = satisfied, 5 = Very satisfied.
4. Proportion of subjects reporting 2-24h headache relief, defined as headache relief at 2 hours without rescue medications, then no moderate to severe headache in the next 22 hours, and no use of rescue medication or additional stimulation.

Additional efficacy analyses that will be performed

1. Proportion of subjects reporting improvement in their MBS other than a headache AND reduction in their pain level, 1 and 2 hours post-treatment initiation (if rescue therapy was not used), in their first eligible treated migraine attack.
2. Proportion of subjects reporting freedom from their MBS other than a headache AND pain free, 1 and 2 hours post-treatment initiation (if rescue therapy was not used), in their first eligible treated migraine attack.
3. Rescue medicine usage.
4. Proportion of subjects who had pain relief in at least 50% of their eligible treated attacks at each timepoint.

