4.3 Modified Intent-to-Treat (mITT) analysis set

The mITT analysis set will include all subjects from the ITT analysis set who treat at least one eligible attack (excluding the "self-practice test"). Subjects in the mITT analysis set will be analyzed as treated.

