4.4 Per-protocol (PP) analysis set

The per-protocol (PP) analysis set will include all subjects in the mITT population who completed at least one eligible attack in compliance with the protocol and have no major protocol deviations. Subjects in the PP population will be analyzed as-treated.

Major protocol deviations defined as deviations which may impact subject safety, alter the risk/benefit ratio, compromise the integrity of the study primary end point data include, but are not limited to:

- Study treatment deviation for first eligible attack, e.g. baseline diary reported after treatment initiation, diary reported after treatment start, Baseline diary reported more than 30 minutes prior to the initiation of

treatment.

- PRO report outside of window for first eligible attack.

4.5

Statistical Analysis of Analysis Sets

As discussed in the introduction section to the SAP, a technical issue may have rendered the study device ineffective for those subjects treated prior to May 31, 2019. Since the treatments may not have been therapeutic, including them in the primary safety analysis may lead to under reporting of safety events. Consequently, the ITT data analysis set will serve as the principal data analysis set for the safety analyses. The safety analyses will also be performed on the Full Analysis set.

The mITT data analysis set will serve as the principal data analysis set for the efficacy analyses.

The primary and secondary efficacy assessments will also be performed on the per protocol (PP) and the ITT analysis sets.

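### No MBS endpoint says how subjects who record no most bothersome symptom are counted, and the only written coding rule, read literally, makes them non-responders

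*Protocol*

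**What the plan says.** Protocol 8.1.6 (Treatment period) has the subject record, before stimulation, the baseline pain level and "the most bothersome migraine-associated symptom (nausea, photophobia, phonophobia or none". The follow-up item concerns the symptom "chosen at baseline) improvement (yes/no) at 1 and 2 hours".

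The endpoint definition names only three symptoms: "MBS may be nausea, photophobia, phonophobia as defined by each subject prior to beginning of the treatment" (Protocol 4.2.2). SAP 2.2, which prevails over the protocol where they differ, repeats this for "Proportion of subjects reporting improvement in their most bothersome migraine-associated symptom (MBS) other than a headache". Neither mentions *none*.

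On coding, Protocol 11.1.2 says "The three secondary endpoints will also be represented in the form of binary variables", each "assigned the value of '1' if the subject is a 'responder' to each specific secondary endpoint, and '0' otherwise".

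On the population, SAP 4.5 says "The mITT data analysis set will serve as the principal data analysis set for the efficacy analyses". SAP 4.3 defines that set as "all subjects from the ITT analysis set who treat at least one eligible attack"; having an MBS is not a condition.

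Additional analyses 7 and 9 in SAP 2.3 take MBS improvement and MBS freedom per attack over all eligible treated attacks. Analyses 10 and 11 in the same list are explicitly limited to patients with moderate or severe pain at baseline.

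**The concern.** The diary foresees attacks without an MBS. Treatment must start within 30 minutes of headache onset and mild baseline pain is allowed, so such attacks are plausible. A subject with no symptom carries no information about symptom improvement. Coded 0 in both arms, such subjects pull both response rates down and shrink the difference between them.

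MBS freedom (exploratory endpoint 1 in the protocol, also in SAP 2.3) and the combined MBS-and-pain analyses have a related gap. A *none* subject could be coded 0, having had no symptom to lose, or trivially 1, having no symptom at 2 hours.

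MBS improvement is one of three secondary endpoints tested after the primary and adjusted together by Benjamini–Hochberg (Protocol 11.7.2). Its p-value can therefore also move the adjusted p-values of the other two. If the denominator is chosen only at analysis, the result depends on a choice that nobody wrote down.

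**Working it through.** **1. The plan's own figure.** Protocol 11.3 gives 45% vs 25%, 80% power and a 5% level; Protocol 11.7.1 makes tests two-sided. With p̄ = 0.35 and d = 0.20:

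n per arm = [1.960·√(2·0.35·0.65) + 0.842·√(0.45·0.55 + 0.25·0.75)]² / 0.20² = (1.322 + 0.555)² / 0.04 ≈ 88.1, rounded up to 89.

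That is 178 in total against the stated 180. Power at 90 per arm is 80.8%, and 180/0.9 = 200. The formula matches, but these figures concern the primary endpoint. No power, response rate or share of *none* is given for the MBS endpoint.

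**2. Assumptions.**
- MBS response rates p₁ and p₂ among subjects with an MBS. 45% vs 25% is borrowed from the primary endpoint; 60% vs 40% and 70% vs 45% show the range.
- A share f of *none*, equal in both arms, from 10% to 30%.
- 109 subjects (SAP Introduction, the number with primary endpoint data), split evenly at 54.5 per arm.

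**3. Effect on the difference.** Coding *none* as 0 gives rates p₁(1−f) and p₂(1−f), so the difference is (p₁−p₂)(1−f). Twenty points become 18, 16 and 14 at f = 10, 20 and 30%. The risk ratio p₁/p₂ does not change.

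**4. Effect on power.** Power = Φ{[d√n − 1.960·√(2p̄(1−p̄))] / √(p₁(1−p₁)+p₂(1−p₂))}. Coded 0 uses the diluted rates with n = 54.5; restricted uses the undiluted rates with n = 54.5(1−f).

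Example at f = 20% and 45% vs 25%:
- Coded 0: 36% vs 20%, n = 54.5, so (1.181 − 1.245)/0.625 = −0.10 and power is 46.0%.
- Restricted: 45% vs 25%, n = 43.6, so (1.321 − 1.322)/0.660 ≈ 0.00 and power is 49.9%.

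| Assumed rates | f | Coded 0 | Restricted | Loss (points) |
|---|---|---|---|---|
| 45% vs 25% | 10% | 52.6% | 54.7% | 2.1 |
| | 20% | 46.0% | 49.9% | 3.9 |
| | 30% | 39.6% | 44.8% | 5.2 |
| 60% vs 40% | 10% | 47.1% | 50.9% | 3.8 |
| | 20% | 39.8% | 46.2% | 6.4 |
| | 30% | 33.3% | 41.4% | 8.1 |
| 70% vs 45% | 10% | 65.6% | 71.3% | 5.7 |
| | 20% | 55.5% | 66.1% | 10.6 |
| | 30% | 46.1% | 60.1% | 14.0 |

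At the planned 90 per arm and 45% vs 25%, power is 74.3/66.9/59.0% coded 0 and 76.6/71.5/65.6% restricted, a loss of 2.3/4.6/6.6 points.

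**5. Unequal shares by arm, *none* coded 0.**
- 45% vs 25%, with 20% *none* in active and 10% in sham: 0.45·0.80 − 0.25·0.90 = 13.5 points. Reversed: 0.45·0.90 − 0.25·0.80 = 20.5 points.
- No true effect, 40% response in both arms, 5% *none* in active and 15% in sham: 0.40·0.95 − 0.40·0.85 = 4 points.

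**The case against.** No sentence assigns 0 to a *none* subject. Protocol 11.1.2 is one generic line for three endpoints and does not discuss denominators. The endpoint wording concerns the subject's own MBS, lists three symptoms and asks about the one chosen at baseline, so a denominator of subjects who named a symptom fits it well. Treating the value as missing, with the optional imputation in Protocol 11.7.5, is a third reading. All of this stands: a reader might infer that the plan instructs failure coding, and the documents do not support that.

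Both documents are abridged, and the SAP's contents end at section 4.5, so a denominator rule may exist in the full plan. This lowers confidence but does not remove the point. The endpoint definitions and analysis sets are in the public SAP, which states a baseline restriction where one is intended (analyses 10 and 11) and none for any MBS endpoint.

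A reader might also infer a biased comparison from the unequal-share figures. The documents give no ground for that. The MBS is recorded before the attack is treated, in a randomised trial with blinded subjects and staff. A difference in *none* between arms would be expected only by chance, adding noise in either direction. With equal shares, coding 0 only shrinks the difference toward zero.

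Finally, restriction also costs power because n falls, so the fair comparison is between the two power columns, not with the undiluted 20 points. The table makes that comparison.

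**Conclusion.** The concern holds as a gap with a literal default. *None* is an allowed answer, no MBS endpoint excludes it, and the only written coding rule, applied to the mITT set, would count such subjects as non-responders on the first secondary endpoint. The per-attack MBS analyses keep such attacks in the denominator in the same way, and for MBS freedom the coding could go either way.

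If the literal rule is applied, the absolute difference shrinks by (1 − share of *none*). The power loss against a restricted denominator is about 2–5 points under 45% vs 25%, 109 subjects and 10–30% *none*. It is larger if MBS response rates are higher. These sizes are illustrations that rest on assumed rates and shares. Importance is low to moderate: the endpoint is secondary and is tested only if the primary succeeds, and the MBS-freedom, combined and per-attack analyses lie outside the testing hierarchy.

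**What to change.** In Protocol 11.1.2 and SAP 2.2–2.3, before unblinding (the SAP Introduction says the data are still blinded):

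- Define the denominator of every MBS endpoint as mITT subjects, or eligible attacks for the per-attack analyses, with nausea, photophobia or phonophobia chosen at baseline of the analysed attack. Apply the same rule to MBS freedom and the combined MBS-and-pain analyses.
- Report the number with *none* in each arm.
- For MBS improvement, give the all-mITT analysis with *none* = 0 as a sensitivity analysis.

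The cost is a sentence or two of text and a somewhat smaller denominator. No new data are needed, because the baseline diary already identifies these subjects.
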